#### *Dynamic Copenhagen Adduction exercise (DCA)*

The CA is performed with the athlete lying on the side. His forearm is used for support on the ground while the other hand rests on the pelvis. The partner supports the training leg by keeping it at the height of their pelvis and holding it with one hand placed under the knee and the other under the ankle. Then the athlete brings the hip of the training leg into adduction until the thigh and the torso form a straight line, while the hip of the other leg is also adducted. Then the hip of the training as well as the non-training leg come into abduction. The non-training leg touches the ground without supporting the body. The duration of the entire movement is 6 seconds (3 seconds of concentric and 3 seconds of eccentric contraction). To ensure correct execution of the exercise, flexion, lateral flexion and rotation movements of the torso and/or hip are avoided. The athlete's effort is supported by vocal instructions from the supervisor. The athlete performs the exercise on both sides.

#### *Isometric Copenhagen Adduction exercise (ICA)*

The isometric Copenhagen adduction exercise will be performed in three progression levels. In the first level, the athlete's training leg is placed on a box with support under the medial surface of the knee, the hip of the non-training leg in adduction, and the knee at 90 degrees of flexion. In the second level, the training leg is placed on a box with support under the medial malleolus, the hip of the non-training leg in abduction, and the knee at 90 degrees of flexion. In the third level, the training leg is placed on a box with support under the medial malleolus, the hip of the non-training leg in adduction, and the knee at 90 degrees of flexion. The athlete's forearm is used for support, while the other hand rests on the pelvis. The duration of each repetition will be 6 seconds. To ensure correct execution of the exercise, flexion, lateral flexion and rotation of the trunk and/or hip will be avoided. The athlete's effort will be supported by vocal instructions from the supervisor. The athlete performs the exercise on both sides. The height of the box which will be used will be 40 cm. In cases where the athlete's humerus is shorter, a 30 cm box will be used.

#### *Training Load*

We will attempt to keep the two exercises as similar as possible throughout the study by keeping the same total repetition number and time under tension, using 2 sets of 6-12 repetitions per side for both exercises. For the DCA, the increase of the repetition number will be the only progression parameter. For the ICA, the lever of the training leg will be used as an additional progression component.

#### *Outcome measures*

The primary outcome measures will be maximal eccentric (EHAD) and isometric (IHAD) hip adduction torque. The secondary outcome measures will be jump (squat jump, countermovement jump, countermovement jump with arm swing) and sprint (5m, 10m, 20m) capacity, delayed onset muscle soreness (DOMS), and perceived exertion. Torque will be

measured using a digital handheld dynamometer (Activforce 2, ActivBody, California, USA) and standardized strength testing (unilateral supine eccentric adduction strength test, unilateral supine isometric adduction strength test). Jump and sprint capacity will be measured using the Microgate Optogait (Microgate, Bolzano, Italy) and Fitlight System (Fitlight USA Inc., Miami, Florida), respectively. Perceived exertion will be recorded for each exercise using the Borg CR10 scale. DOMS will be recorded before the start of each exercise session, referring to the previous session, with the use of a numerical ranking scale (0-10).

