## Methods

### *Inclusion criteria*

Healthy male players aged between 12 and 16 years old systematically ( $\geq 4$  times per week) participating in training and games will be eligible for inclusion.

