### *Training groups*

The participants will be assigned to either a dynamic (DCA) or an isometric (ICA) Copenhagen Adduction exercise group and will perform a progressive exercise protocol for 6 weeks during

the in-season of the team at the club's training facilities. Both exercises will be performed twice per week with a 48-hour rest between them.

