#### *Statistical analysis*

Statistical analysis will be performed using SPSS Statistics (v26, IBM Corporation). Baseline and follow-up values will be presented as mean  $\pm$  standard deviation (SD). For torque, jump, and sprint analysis, the highest value will be used. One-way ANCOVA will be used for between-group differences on the dependent variables (EHAD, IHAD, jump, sprint), while paired samples t-test will be used to determine the difference between baseline and follow-up values for the dependent variables (EHAD, IHAD, jump, sprint). Repeated measures ANOVA with Bonferroni correction will be used to determine the difference between groups for DOMS and perceived exertion. Athletes with compliance less than 75% of the total number of sessions will be excluded from the statistical analysis. Effect size (Cohen's d) is calculated will be set as small (0.2), moderate (0.5), and large (0.8), while statistical significance as  $p \leq 0.05$ .

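### No soreness rating is defined before the first trial exercise session, so the DOMS comparison forgoes a pre-exposure value to adjust for

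*Combined protocol and SAP*

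**What the plan says.** DOMS is a secondary outcome; the Outcome measures section lists "delayed onset muscle soreness (DOMS), and perceived exertion" with jump and sprint. The timing rule there is "DOMS will be recorded before the start of each exercise session, referring to the previous session", on a 0 to 10 scale. It makes no exception for session 1 and mentions no separate baseline soreness rating. Neither the muscle group nor the recall window is given.

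On the schedule, the Training groups section says that players "will perform a progressive exercise protocol for 6 weeks during" the season, and that "Both exercises will be performed twice per week with a 48-hour rest between them". The setting is "the in-season of the team at the club's training facilities". The Inclusion criteria section requires players who, at least four times a week, are "participating in training and games will be eligible for inclusion".

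On the analysis, the Statistical analysis section says "Repeated measures ANOVA with Bonferroni correction will be used to determine the difference between groups for DOMS and perceived exertion". It does not list the time points and has no baseline term for DOMS. The ANCOVA and the baseline to follow-up t-tests are limited to torque, jump and sprint.

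The nearest pre-intervention pain item is the exclusion for pain above 2/10 during testing or the intervention. That is a threshold screen and not a recorded soreness value. It admits players with pain up to 2/10.

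**The concern.** The timing rule cannot be followed at session 1, because each rating must look back to an earlier trial session and none exists. The person recording it could leave the slot blank, enter 0, or record soreness from football, and the plan does not choose.

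- A blank discards the only possible pre-exposure measurement. If that slot is still entered as a time point, a standard repeated measures ANOVA, which needs complete rows, drops the player.
- A zero is an invented value. It has no variance and builds in a time effect between session 1 and the later ratings.
- Football soreness is a useful measurement. Analysed as an outcome, however, it is a value that no trial exercise could have caused.

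Players in mid-season can be expected to carry some soreness into the trial, and they differ in how they use a 0 to 10 scale. Without a pre-exposure value, that variation between players stays in the error term of the group comparison, and a chance difference between the groups cannot be seen. The absolute soreness level in each arm also has no reference against which to separate the exercise's contribution from football's.

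**Working it through.** The plan gives no sample size, standard deviation or effect size for DOMS, so it has no figure of its own to reproduce. The check is a count of the schedule and two short calculations.

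**1. Ratings with a referent.** Inputs: 6 weeks and 2 sessions a week (Training groups).
- Planned sessions: 6 × 2 = 12, so 12 pre-session ratings if the rule is read literally.
- The rating before session k refers to session k − 1. For k = 1 there is none. For k = 2 to 12 the referents are sessions 1 to 11.
- Ratings with a referent: 12 − 1 = 11.

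**2. Background exposure.** Input: at least 4 training sessions or games a week (Inclusion criteria). Over 6 weeks this is at least 4 × 6 = 24. Whether that count would include the 12 trial sessions is not stated.

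**3. What each reading of the rule gives.**

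| Reading | Session 1 | Later ratings | Pre-exposure value defined? |
|---|---|---|---|
| Literal: a rating before every session | Scheduled, nothing to refer to | Refer to the trial exercise | No; the slot exists but its content is undefined |
| Natural: ratings start at session 2 | Not taken | Refer to the trial exercise | No |
| The session referred to is team training | Has a referent | No longer measure soreness from the trial exercise | Only at the cost of the outcome's meaning |

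**4. Precision forgone.** Let r be the correlation between the pre-exposure rating and a player's later ratings. The documents give no value, so r is an assumption. Adjustment cuts between-player variance by about r², and the equivalent sample size multiplier is 1/(1 − r²).

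| Assumed r | Variance cut, r² | 1/(1 − r²) | Equivalent extra players |
|---|---|---|---|
| 0.1 | 1% | 1/0.99 = 1.01 | about 1% |
| 0.2 | 4% | 1/0.96 = 1.04 | about 4% |
| 0.3 | 9% | 1/0.91 = 1.10 | about 10% |
| 0.5 | 25% | 1/0.75 = 1.33 | about 33% |

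**5. Dilution if session 1 is analysed as an outcome.** Let d be the mean group difference over the 11 ratings that can carry an effect. The expected difference at session 1 is zero. The average over 12 equally weighted time points is (11 × d + 0)/12 = 0.917d, a shrinkage of 1/12 = 8.3%. This applies to the group effect averaged over time. It is not a loss of power of the same size, and the group-by-time term is not diluted in this way.

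**The case against.** The strongest reply is that the rule reads naturally as starting at session 2, when a previous trial session first exists. A blank at session 1 is then correct practice, 11 ratings are valid, and there is nothing to mishandle. The trial runs in one club setting with a small supervising team, so whatever is done at session 1 is likely to be done alike in both arms. This largely stands. It removes the worry about inconsistent recording, but it leaves no pre-exposure value.

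A second reply is that soreness attributed to a given exercise session cannot exist before that exercise, and perceived exertion has no baseline either. The comparison with torque and jump is therefore imperfect. This also stands in part: current adductor soreness is a related covariate and not the same quantity measured earlier. A covariate need not be the same quantity to be useful, but the difference is a reason to expect a lower correlation. So are the exclusions for recent adductor injury, recent adductor strength training and pain above 2/10, which may push baseline scores towards zero. For this reason the range above starts at 0.1.

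A reader might infer that background football soreness will be mistaken for a treatment effect and that the DOMS comparison is biased. The documents do not support that. Players are randomised, so background soreness and rating habits are balanced in expectation. Residual chance imbalance is what the standard error and p-value allow for, and the unadjusted comparison remains valid.

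A reader might also infer that the estimate will be diluted by 8%. That follows only if the session 1 rating is entered as an outcome, and the Statistical analysis section does not say that it is.

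**Conclusion.** The point holds as a gap in definition and a missed gain in precision. On the literal schedule 11 of 12 ratings have a referent, and on no reading does the plan define a pre-exposure soreness value while keeping DOMS tied to the trial exercise.

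What is forgone is efficiency, a check on chance imbalance, and a reference level for interpreting the absolute scores. The efficiency gain ranges from negligible to worthwhile (about 1% to 33% in equivalent sample size) and rests entirely on the assumed correlation of 0.1 to 0.5. The 8% shrinkage is conditional on how session 1 is handled.

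DOMS is secondary, so the trial's primary conclusions are not affected. The change is still worth making before the first session, because a pre-exposure rating cannot be collected afterwards.

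**What to change.** In Outcome measures, state: *Before session 1, and before the group is announced, each player rates current adductor soreness from 0 to 10; this is the baseline. From session 2 on, DOMS is adductor soreness attributed to the previous trial exercise session.* The order matters because the Randomization section has players learn their group on the day of session 1. A rating taken after that could be coloured by knowing it.

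In Statistical analysis, state: *The session 1 rating enters the DOMS repeated measures analysis as a covariate and is not one of the outcome time points, which are the ratings before sessions 2 to 12.*

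The cost is one question per player, at a point where the literal schedule already has a rating, and one covariate degree of freedom. No visit is added and the exercise programme is unchanged. The downside is little gain if baseline scores cluster near zero.

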#### *Statistical analysis*

Statistical analysis will be performed using SPSS Statistics (v26, IBM Corporation). Baseline and follow-up values will be presented as mean  $\pm$  standard deviation (SD). For torque, jump, and sprint analysis, the highest value will be used. One-way ANCOVA will be used for between-group differences on the dependent variables (EHAD, IHAD, jump, sprint), while paired samples t-test will be used to determine the difference between baseline and follow-up values for the dependent variables (EHAD, IHAD, jump, sprint). Repeated measures ANOVA with Bonferroni correction will be used to determine the difference between groups for DOMS and perceived exertion. Athletes with compliance less than 75% of the total number of sessions will be excluded from the statistical analysis. Effect size (Cohen's d) is calculated will be set as small (0.2), moderate (0.5), and large (0.8), while statistical significance as  $p \leq 0.05$ .

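### Taking the largest value for sprint selects each player's slowest run if sprint is scored as time, and the plan does not say how it is scored

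*Combined protocol and SAP*

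**What the plan says.** The Statistical analysis section gives a single rule for choosing the value to analyse: "For torque, jump, and sprint analysis, the highest value will be used". It makes no exception for sprint.

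Under Outcome measures, sprint is a secondary outcome described only as "sprint (5m, 10m, 20m) capacity". The measuring equipment is named ("Jump and sprint capacity will be measured using the Microgate Optogait (Microgate, Bolzano, Italy) and Fitlight System (Fitlight USA Inc., Miami, Florida), respectively"), but not the quantity it records. The available text gives no unit, no conversion to speed and no number of runs per distance, and nowhere says that the fastest run or lowest time is meant. The primary outcomes in the same section are "maximal eccentric (EHAD) and isometric (IHAD) hip adduction torque".

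The selected sprint value enters three parts of the analysis:

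- the descriptive summary ("Baseline and follow-up values will be presented as mean", with SD);
- the between-group comparison ("One-way ANCOVA will be used for between-group differences on the dependent variables (EHAD, IHAD, jump, sprint");
- the within-group comparison ("paired samples t-test will be used to determine the difference between baseline and follow-up values").

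**The concern.** Torque and jump normally improve upwards, so the largest of several attempts is the best one. Time over a fixed distance improves downwards, so its largest value is the worst attempt. Sprint is the one outcome under this rule whose natural raw measure runs in the opposite direction.

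An analyst who applies the sentence literally to columns of sprint times would carry each player's slowest 5, 10 and 20 m runs into the means, SDs, ANCOVA and paired t-tests. That does not fit an outcome called capacity, and it sits oddly beside torque outcomes called maximal. An analyst who quietly took the lowest time instead would be analysing what was probably intended, but would be departing from the written plan. The published sprint figures could therefore describe either the best or the worst run, and a reader with only the plan could not tell which.

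**Working it through.** The plan states no figure on this point, so there is none to reproduce. The check has three steps.

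**1. Does the rule depend on the scale?** Speed = distance / time. At a fixed distance the two scales rank the runs in opposite order. Take three invented 20 m times:

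| Run | Time (s) | Speed = 20 / time (m/s) |
|---|---|---|
| A | 3.10 | 6.45 |
| B | 3.18 | 6.29 |
| C | 3.25 | 6.15 |

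The highest time is run C, the slowest. The highest speed is run A, the fastest. The same sentence selects opposite runs on the two scales.

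**2. How far apart are the two selections?** Suppose a player makes *k* runs with independent normal error of standard deviation σ. The expected gap between slowest and fastest is the expected range, 2 × E[max of *k* standard normals] × σ. Neither *k* nor σ is in the documents, so both are assumed: *k* = 2 to 4 and σ = 0.02 to 0.05 s, with the same σ range at all three distances.

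| Runs (*k*) | Gap in σ | σ = 0.02 s | σ = 0.03 s | σ = 0.05 s |
|---|---|---|---|---|
| 1 | 0 | 0 | 0 | 0 |
| 2 | 1.1284 | 0.023 s | 0.034 s | 0.056 s |
| 3 | 1.6926 | 0.034 s | 0.051 s | 0.085 s |
| 4 | 2.0588 | 0.041 s | 0.062 s | 0.103 s |

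For example, with *k* = 3 and σ = 0.05 s: 1.6926 × 0.05 = 0.085 s. With a single run the rule has no effect.

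**3. Does it bias the comparisons or change precision?** The gap is a shift in level. If the number of runs and the run-to-run variability are the same in both groups and at both visits, the shift cancels from the group difference and from the change over time.

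A simulation of 400,000 players tested this. All inputs were assumed: between-player SD 0.15 s, run SD 0.05 s, SD of true change 0.05 s, and a true mean change of zero. The mean change stayed within 0.001 s of zero under both rules.

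For precision, the measure is the ratio of ANCOVA residual variance, highest time over lowest time. A ratio above 1 means the highest time is the noisier choice. The occasional errors affected 2% to 10% of runs, with a mean size of 0.1 to 0.2 s.

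| Run-to-run error | 2 runs | 3 runs |
|---|---|---|
| Symmetric | 1.00 | 1.00 |
| Occasional slow-side errors added | 1.18 to 3.90 | 1.28 to 5.64 |
| Occasional fast-side errors added | 0.84 to 0.26 | 0.78 to 0.18 |

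The ratio moves either way with the type of error assumed. The documents do not say which type applies, so no loss or gain of precision is claimed.

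**The case against.** The strongest reply is that this is loose wording and not an analysis error. The harmful reading needs two facts the documents do not supply: that sprint is scored as time, and that each distance is run more than once. The word capacity suggests a scale on which more is better, and hardly anyone would set out to analyse each player's worst run. In practice the analyst would probably take the fastest. Even on the bad reading there is no bias from the rule itself and no demonstrable loss of precision. What remains is a shift in the reported level of three secondary outcomes, and its size in seconds rests on assumed inputs.

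Much of this stands. Time scoring is unconfirmed, best performance is the likely intent, and the figures in seconds are illustrative. The cancellation also needs equal run-to-run variability in both groups and at both visits, as well as equal numbers of runs.

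It does not remove the point. This sentence is the plan's only selection rule for these data, and choosing a highest value makes sense only with repeated attempts. On the most natural scale for a timed sprint, it names the wrong run. That the intent can be guessed is a reason to correct the text, because following the guess means departing from the plan as written.

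**Conclusion.** The concern holds, as a minor one. The rule covers sprint, no sprint unit is given, and a time score would make the selected value the slowest run.

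On that reading, and with 2 to 4 runs per distance, the analysed sprint value would be an average of 1.13 to 2.06 within-player SDs slower than the fastest run. That is about 0.02 to 0.10 s if the run-to-run SD is 0.02 to 0.05 s. The SD multiples assume normal error and an assumed number of runs; the seconds also depend on an assumed SD.

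The effect is confined to the 5, 10 and 20 m results. The primary torque outcomes, jump, soreness and perceived exertion are untouched. If sprint is scored as speed, or run once per distance, the rule does no harm.

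**What to change.** Replace the sentence in the Statistical analysis section with: *For torque and jump the highest value, and for sprint time at each distance the lowest (fastest) value, will be used.* Alternatively, state that sprint is analysed as speed in m/s and keep the highest value for all three.

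With either wording it would help to give the sprint unit and the number of runs per distance under Outcome measures, with the same number at both visits. The correction itself does not depend on that addition.

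The cost is one sentence. Randomisation and the statistical models stay as they are. Data collection is also unchanged, provided the number of runs is already the same at both visits.

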### *Exclusion criteria*

- (1) musculoskeletal injury and/or neurological disorder that would affect strength and/or athletic performance testing, and/or the exercise execution.
- (2) adductor muscle injury within 6 months before study initiation.
- (3) pain greater than 2/10 on a Numeric Rating Scale (NRS) during strength and/or athletic performance testing, and/or during the intervention.
- (4) any systematic strength training of the adductor muscles during the last month prior to study initiation.

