### *Randomization*

Randomization will be performed before baseline testing with the use of an online software (<https://randomizer.org/>) by a person that will not otherwise be involved in the study. The randomization result for each participant will be placed in a numbered sealed opaque envelope and be given to the physiotherapist and the exercise therapist who will supervise the intervention. The group allocation will be announced to every participant the day of the first exercise session.

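### Excluding players below 75% compliance from the only planned analysis removes the protection of randomisation from the EHAD and IHAD comparisons if any player falls short

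*Combined protocol and SAP*

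**What the plan says.** All references are to the combined protocol and SAP.

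- **Statistical analysis.** After naming ANCOVA, paired t-tests and repeated measures ANOVA, the section gives one rule for who is analysed: "Athletes with compliance less than 75% of the total number of sessions will be excluded from the statistical analysis". The rule is not confined to a secondary or per-protocol analysis. The document describes no all-randomised set, sensitivity analysis or missing-data method.
- **Outcome measures.** "The primary outcome measures will be maximal eccentric (EHAD) and isometric (IHAD) hip adduction torque". The rule therefore decides who enters both primary comparisons.
- **Training groups.** The programme lasts 6 weeks, and "Both exercises will be performed twice per week with a 48-hour rest between them".
- **Randomization.** "Randomization will be performed before baseline testing with the use of an online software", and "The group allocation will be announced to every participant the day of the first exercise session".
- **Exclusion criteria.** One criterion is "pain greater than 2/10 on a Numeric Rating Scale (NRS) during strength and/or athletic performance testing, and/or during the intervention". Its last part can be met only after a player has been randomised. The plan does not say whether such a player's data stay in the analysis.

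**The concern.** Randomisation makes the two groups comparable as allocated. It gives no such assurance for subgroups defined by something that happens later. Attendance is a later event, and players who know which exercise they are doing can attend differently because of it.

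Differential attendance is plausible here. The arms differ in contraction mode, and the isometric arm progresses through lever length as well as repetitions (Training Load). Soreness and exertion are themselves compared between the arms, so the plan treats tolerability as an open question. The pain criterion may be a second way out of the analysis after randomisation.

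If low attenders would also have tested differently, dropping them shifts the group means by amounts that need not cancel. Adjusting for baseline torque removes only the part of the selection that baseline explains. With a single analysis set, nobody can see afterwards whether the conclusion depends on the exclusions. If low attenders are not tested at follow-up, their outcomes cannot be recovered.

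**Working it through.** The plan states no sample size, SD, target difference or expected attendance, so it has no figure to reproduce.

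**Step 1: the threshold.** 6 weeks × 2 sessions = 12 sessions, and 0.75 × 12 = 9. A player with 8 or fewer sessions is removed. This reads compliance as attendance; the plan does not define the word.

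**Step 2: the order of events.** Randomisation comes first, then baseline testing, then disclosure of the arm on the day of the first session, then 12 sessions, then follow-up testing. Everything that decides the exclusion comes after allocation.

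**Step 3: possible size. Every input is an assumption.**
- No true difference; two-sided 0.05 for each outcome (the plan does not state sidedness).
- 20, 30 or 50 players randomised per arm.
- The baseline-adjusted outcome is standard normal and correlates ρ with a latent attendance propensity.
- A share q of each arm is excluded from the lower tail of that propensity.

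The mean of the retained players in an arm shifts by ρ × m(q), where m(q) = φ(z_q)/(1 − q):

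| q | m(q) |
|---|---|
| 5% | 0.1031/0.95 = 0.109 |
| 10% | 0.1755/0.90 = 0.195 |
| 20% | 0.2800/0.80 = 0.350 |
| 25% | 0.3178/0.75 = 0.424 |

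Bias = ρ × [m(q1) − m(q2)]. For example, 20% against 10% at ρ = 0.5 gives 0.5 × (0.350 − 0.195) = 0.077 SD (unrounded inputs). Type I error comes from the non-central t distribution with the retained numbers per arm.

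| Excluded | ρ | Bias (SD) | Type I error, n = 20 / 30 / 50 |
|---|---|---|---|
| Equal shares, same ρ | any | 0 | 0.050 throughout |
| 10% v 5% | 0.3 | 0.026 | 0.051 / 0.051 / 0.052 |
| 10% v 5% | 0.5 | 0.043 | 0.052 / 0.053 / 0.055 |
| 20% v 10% | 0.3 | 0.046 | 0.052 / 0.053 / 0.055 |
| 20% v 10% | 0.5 | 0.077 | 0.056 / 0.058 / 0.064 |
| 25% v 5% | 0.1 | 0.032 | 0.051 / 0.051 / 0.052 |
| 25% v 5% | 0.3 | 0.095 | 0.058 / 0.063 / 0.071 |
| 25% v 5% | 0.5 | 0.158 | 0.073 / 0.085 / 0.110 |

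**Step 4: check by simulation.** ANCOVA on simulated data (20,000 runs per cell, assumed baseline correlation 0.7, n = 20 and 50, ρ = 0.3 and 0.5) gave:
- 10% v 10%: bias −0.004 to 0.003, error 0.048 to 0.051
- 10% v 5%: bias 0.024 to 0.045, error 0.049 to 0.054
- 20% v 10%: bias 0.043 to 0.077, error 0.050 to 0.066
- 25% v 5%: bias 0.095 to 0.158, error 0.057 to 0.111

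**Step 5: equal exclusion is not always safe.** If 10% are excluded in each arm but ρ is 0.5 in one and 0 in the other, the bias is 0.5 × 0.195 = 0.10 SD.

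**Scale.** The plan calls an effect of 0.2 small but does not say which SD its Cohen's d uses. The figures above are in SDs of the baseline-adjusted outcome. In SDs of the raw outcome, at a baseline correlation of 0.7, they shrink by √(1 − 0.7²) = 0.71, so 0.158 becomes 0.11.

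**The case against.** The best counter-argument is that the expected damage is small. In the mild cases the bias is 0.03 to 0.04 SD and the type I error at most 0.055. Only the severe case reaches 0.10 SD or more when ρ is the same in both arms, and even that case is trivial at ρ = 0.1. Sessions are supervised and held at the club, players already train or play at least four times a week, and the plan aims at "keeping the same total repetition number and time under tension" in both arms. If everyone completes 9 sessions, the rule changes nothing. It is also set in advance, identical in both arms and based on sessions rather than results, and the strength and performance testers do not know the allocation.

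All of this is fair, and it limits what can be claimed about size. Loss of protection means that balance is no longer guaranteed, not that bias is certain. It is also true that ANCOVA deals with selection that runs through the covariate, presumably baseline torque. What remains is selection on whatever baseline does not explain. The pain criterion is an ambiguity rather than a stated exclusion from analysis.

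None of this supports keeping the rule as the only analysis. A rule that is the same for both arms can still select differently within them, and blinded testing does not affect who is dropped. If attendance is high, analysing everyone costs almost nothing; if it is not, the all-randomised analysis is needed. If the aim is the effect in players who adhere, the plan does not say so, and a per-protocol analysis can serve that aim.

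**Conclusion.** The concern holds. Followed exactly, the plan bases both primary comparisons on a set selected after randomisation whenever a player falls below 9 of 12 sessions, and it offers no other set against which to check the result.

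This conclusion rests on the wording of the rule and the order of events, not on the numerical illustration. Neither the direction nor the size of bias can be derived from the documents. Under the assumptions shown, it runs from zero to about 0.16 SD, with type I error from 0.050 to 0.110; the larger values need both strongly unequal exclusion and a correlation near 0.5. The range is illustrative and not an upper bound. The change should be made before follow-up testing, because outcomes not measured then cannot be recovered.

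**What to change.** In the Statistical analysis section:

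1. Make the primary EHAD and IHAD analysis one of all randomised players in their assigned group, whatever their attendance.
2. Invite every player to follow-up testing, including low attenders and those who stop training.
3. State how missing tests are handled. One option is multiple imputation using arm, baseline torque and sessions attended, with a sensitivity analysis shifting the imputed values in one arm at a time, for example by 0.1 to 0.5 SD. The model and range are suggestions.
4. State that a player who meets the pain criterion after randomisation stays in the primary analysis set. This concerns the analysis set only, not whether he goes on training.
5. Define compliance, and report attendance and exclusions by arm with reasons.
6. Keep the 75% set as a labelled per-protocol sensitivity analysis.

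Soreness and exertion are recorded at sessions, so follow-up testing cannot recover missing values for them; their handling needs its own sentence.

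**Cost.** New wording, plus follow-up tests for low attenders, whose number cannot be stated without a sample size or dropout rate. The statistical price is dilution of a true difference. If a share q in each arm attends poorly and shows a fraction f of the full difference, the estimate is 1 − q(1 − f) of it. With f assumed between 0 and 0.5, that is 0.90 to 0.95 at q = 10% and 0.80 to 0.90 at q = 20%. The per-protocol estimate is still reported.
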